#### 4.1.6 RPPA data

Normally distributed unpaired RPPA data (WINGMEN\_DataDefinitions&Tables Section 5.2.4 and Figure 9) will be analysed for the most significantly deregulated proteins using the methods described in Section 4.1.3.

### 4.2 Definition of Analysis Populations

See WINGMEN\_DataDefinitions&Tables Section 3.

## 5 TRIAL POPULATION AND DESCRIPTIVE ANALYSES

*Summary of flow of trial participants through the trial and baseline stratification, demographic and clinical characteristics of each group.*

### 5.1 Representativeness of Study Sample and Patient Throughput

#### 5.1.1 Representativeness of study sample

Subjects recruited to this trial will be fit (performance status 0-1) and thus representative of men scheduled for radical prostatectomy. For inclusion, the patient must have sufficient tumour in the diagnostic biopsy to provide at least 2 tissue sections for primary endpoint assessment. This criterion will be fulfilled for the majority of men whose prostate cancer is suitable for treatment by radical surgery. Exclusion criteria include:

- Treatment with systemic corticosteroids, insulin, metformin, other oral hypoglycaemic agent, or anti-androgens in the 28 days prior to first dose of study drug
- Diabetes mellitus
- Previous prostate radiotherapy
- Current or previous treatment with xentuzumab or other IGF or GH -modifying therapy
- Patients who are known to be serologically positive for Hepatitis B, Hepatitis C or HIV
- Treatment with any other investigational agent, or treatment in another interventional clinical trial within 28 days prior to enrolment
- Other psychological, social or medical condition, physical examination finding, or laboratory abnormality that the Investigator considers would make the patient a poor trial candidate or could interfere with protocol compliance or the interpretation of trial results.

#### 5.1.2 Patient Throughput

See WINGMEN\_DataDefinitions&Tables Section 4.2, Table 5, and Appendix 1: CONSORT Flow Diagram. The CONSORT flowchart will provide an overview, but additional expansion of reasons and timing of withdrawals from the study may be required.

### 5.2 Withdrawal from Treatment and/or follow-up

This information will be included in WINGMEN\_DataDefinitions&Tables Section 4.2, Table 5, and Appendix 1: CONSORT Flow Diagram. No statistical tests will be used here. If patients withdraw early, their research blood and tissue samples will still be used for analysis if the patient gives consent.

### 5.3 Baseline Characteristics

Trial subjects' baseline characteristics will be tabulated as in WINGMEN\_DataDefinitions&Tables Section 4.1 and Table 4. There will be no stratification by treatment group. Numbers (with percentages) for binary and categorical variables and mean (and standard deviation), or median (with lower and upper quartiles) for continuous variables will be presented. There will be no tests of statistical significance nor confidence intervals for differences between randomised groups on any baseline variable.

## 5.4 Unblinding

Not applicable: all trial subjects will receive the investigational medicinal product (IMP).

## 5.5 Treatment Compliance with Details of Intervention

The intervention being assessed in this trial is the IMP xentuzumab (Boehringer Ingelheim), an insulin-like growth factor (IGF) neutralising antibody. The drug is administered by intravenous infusion over one hour, once weekly for 4 weeks prior to standard of care radical prostatectomy. Trial subjects whose surgery is delayed will continue to receive weekly xentuzumab for up to 10 cycles in total. The final dose must be given within 6 days of surgery.

Compliance and adherence to the protocol will be assessed by:

- Ability to attend for trial treatment on a weekly basis  $\pm$  1 day of scheduled treatment visits. Incidence of delayed cycles and reasons for delay will be recorded as in WINGMEN\_DataDefinitions&Tables Section 4.2 and Table 5.
- Ability and agreement to provide samples of blood and tissue for research.
- Attendance for a post-xentuzumab blood sample (1-3 days before surgery) at the same time of day and interval after last meal ( $\pm$  2-3 hr) as the pre-xentuzumab blood sample. This is important for consistency of metabolomic profiling.

## 5.6 Reliability

*Note: This section should detail how the reliability of any variables, particularly outcomes, will be checked, for example those derived from raw data. Calculations performed by a computer program may be checked by hand calculations or confirmed by comparison with other measures. This also applies to calculations made to replace missing data.*

**Note:** In the case of different assessors recording data, specify how inter-rater reliability will be assessed and any steps taken in analysis to allow for variations.

### 5.6.1 Primary endpoint markers

Staff of the Translational Histopathology Lab (THL) have assessed and optimised the primary endpoint markers phospho-IGF-1R and phospho-S6 by IHC using control cell samples generated in the [name] lab and tissue samples including tissue microarrays, prostatectomy sections, and prostate biopsies. The results are summarised in the THL Validation Report and confirm stable antibody performance over triplicate independent staining runs. Tests were also carried out to check stability of phospho-IGF-1R and phospho-S6 epitopes by comparing the intensity and distribution of endpoint marker signal in diagnostic biopsy and in-theatre core of a non-trial patient. An example is shown in WINGMEN\_DataDefinitions&Tables Figure 1.

### 5.6.2 Secondary endpoints

Feasibility of treatment in the pre-operative setting, and safety and tolerability of xentuzumab administered in the pre-prostatectomy setting, will use standard clinical metrics including safety data assessed according to NCI-CTCAE v5.0.

### 5.6.3 Research/tertiary endpoints

Tertiary endpoints will be assessed in the [name] lab, Translational Histopathology Lab, the [name] Research Chemistry lab, and the Azenta Sequencing Facility using tested, standardised protocols.

#### 5.6.3.1 Tissue endpoints

The reliability of research/tertiary IHC (e.g. Ki67, IGF-1R, RRM2, CD31) and TMPRSS2-ERG FISH will be checked by including positive and negative controls in each staining run. The signal will be quantified using HALO (WINGMEN\_DataDefinitions&Tables Sections 4.3.1, 5.2.1 and 5.2.3) and reviewed with trial pathologist [name] to check: staining of controls (e.g. cell pellets as shown in WINGMEN\_DataDefinitions&Tables Figure 1A), technical quality of tissue staining, and whether pathological appearances are accurately represented by the HALO data.

#### 5.6.3.2 Circulating endpoints

Paired PRE/POST serum samples will be tested for IGF bioactivity using a validated protocol obtained from Boehringer Ingelheim and used to assess the effect of xentuzumab in the Boehringer Ingelheim-sponsored Phase I trials [6]. Paired samples will be tested in the same assay run, and each assay will include a dose response of recombinant IGF-1, and the results in serum samples expressed as IGF-1 equivalents.

#### 5.6.3.3 PBMCs

Immunoprofiling of peripheral blood mononuclear cells (PBMCs) will be performed either by flow cytometry or CyTOF. The latter will use Standardised Operating Procedures developed and validated by [name] (Research Associate and CyTOF Facility manager, Kennedy Institute of Rheumatology).

#### 5.6.3.4 RNA-seq data

RNA derived from the FFPE-extracted tissue sections will undergo a series of quality checks. First the RNA quantity and purity will be tested in the [name] lab. On receipt at Azenta, RNA quantity will be rechecked, and the RNA integrity number (RIN) measured by TapeStation (Agilent). Azenta Standard Operating Procedures (SOPs) undergo regular review and all instruments are regularly calibrated and maintained, with records recorded in calibration and maintenance logs. Reagent and materials (including lot numbers) are tracked, laboratory staff are trained to the level required for clinical research, and IT systems are regularly maintained and backed up. The data will be analysed and cross-checked by two bioinformaticians in the [name] group, and the analysis will include checks on the expression of specific 'indicator' genes known to be IGF-regulated.

#### 5.6.3.5 Metabolomics

Metabolomic profiles will be assessed on paired PRE/POST sodium heparin plasma using methods described in [7].

## 6 ANALYSIS

*Statistical methods to be used to compare groups for primary and secondary outcomes and methods for point and interval estimation. Include methods for additional analyses, such as adjusted analyses and subgroup analyses, together with which populations will be analysed.*

**Note:** *It may be appropriate to list the outcome definitions, analysis methods, missing data and sensitivity analyses separately for each primary and secondary outcome to be analysed.*

Section 4 above describes the methods that will be used to assess statistical significance of differences in endpoint marker signal between samples taken pre- and post- xentuzumab.

The primary endpoint will be assessed by HALO analysis of 2 immunohistochemical (IHC) markers: phospho-IGF-1R and phospho-S6 (see WINGMEN\_DataDefinitions&Tables Figure 1 and Appendix 2). The scanned IHC images will be quantified using HALO by DPhil student [name] ([name] lab), and HALO data

will be reviewed with trial pathologist [name] as described in Section 5.6 above. Depending on the results of this assessment, we may use mean percentage change in one or both markers to quantify the amount of IGF axis inhibition. This measure will be used in correlation analyses with research/tertiary endpoints in both the entire population and in pre-defined subgroups as described in WINGMEN\_DataDefinitions&Tables Section 5.3 and 5.3.1.

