Full Title of study:	Windows trial of I nsulin-like G rowth factor neutralising antibody Xentuzumab in M EN scheduled for radical prostatectomy	
Short Title:	IGF inhibition with xentuzumab prior to radical prostatectomy	
Trial Acronym:	WINGMEN	
Clinical Phase:	Phase 0	
Study Design:	Open label, 'window of opportunity' study	
Number of Centres	Single centre	
	Objectives	Endpoints
Primary Endpoint:	Assess the amount of IGF pathway inhibition induced by xentuzumab	Phospho-IGF-1R and phospho-AKT (or downstream target) immunohistochemistry on tissue from biopsy and prostatectomy
Secondary Endpoints:	1. Feasibility of treatment in pre-operative setting 2. Assess safety and tolerability of xentuzumab administered in the pre-prostatectomy setting	1. Number of patients whose radical prostatectomy is performed on schedule after 3 doses of xentuzumab (patients can receive up to 10 doses of xentuzumab if surgery is delayed) 2. Treatment-related adverse events scored using CTCAE v5.0
Tertiary/exploratory Endpoints	1. Assess change in PSA following administration of xentuzumab in the pre-prostatectomy setting 2. Assess changes in tissue markers following administration of xentuzumab in the pre-prostatectomy setting 3. Assess changes in circulating markers following administration of xentuzumab in the pre-prostatectomy setting 4. Correlate changes in IGF-1R expression, IGF axis activity with baseline and post-treatment cancer profile, which may include PTEN status by IHC, tumour mutation status, transcriptional, immune and phospho-proteomic profile	1. Change in serum PSA 2. Changes by IHC and/or immunofluorescence on FFPE tissues in tissue markers e.g. Ki67 index, IGF-1R, RRM2, CD31, immune markers PD-L1, CD4, CD8, FoxP3 3. Changes in circulating markers of response to IGF blockade e.g. IGF-1, insulin, IGFBPs, serum IGF bioactivity, metabolomic profile, PBMC immunoprofiling Tumour profiling eg by gene mutation panel, IHC for PTEN, FISH for TMPRSS2-ERG, transcriptional and phospho-proteomic profile, quantification of immune cell infiltration.
Planned enrolment:	20-30 patients	
Target Population:	Men with localised biopsy proven prostate adenocarcinoma, scheduled to be treated by radical prostatectomy.	
Investigational Medicinal Product(s)	Name of drug	Formulation, dose, route of administration
	Xentuzumab	Solution for infusion, 1000mg weekly, IV
Dates for planned trial period	Aug 2021- Apr 2023	

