Statistical significance of the difference between IGF1 axis activity in PRE and POST treatment samples.	
PRE/POST HALO scores will be analysed using a paired t-test, or, if the paired differences do not follow a normal distribution, the Wilcoxon matched pairs signed rank test.
 
Sensitivity analyses: Data will be tested for normal distribution and the appropriate test chosen accordingly (i.e. there is no assumption of normality). The appropriate sample size for 80% power was calculated as in Section 1.4.

Strategies defined in E9 (R1) include treatment policy, while on treatment, principal stratum and hypothetical

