#### 4.1.1 Primary endpoint analysis

PRE/POST FFPE tissue biopsy sections stained for phospho-IGF-1R and phospho-S6 will be scanned and analysed on the HALO platform. This is a deep-learning convolutional neural network that generates H-Scores, representing the sum of the % tissues staining 0 (negative), 1+, 2+ and 3+ to generate a score range of 0-300. If the staining intensity is not sufficient to define a scoring range for H-Scores, percentage of positively stained cells will be used as output instead. To assess the significance of differences before and after xentuzumab, the PRE/POST HALO scores will be analysed using a paired t-test, or, if the paired differences do not follow a normal distribution, the Wilcoxon matched pairs signed rank test. Phospho-IGF-1R staining patterns will also be assessed by [name], to semi-quantitatively score signal in the plasma membrane, cytoplasm and nucleus. Existing data from our group suggest that nuclear IGF-1R associates with higher stage prostate cancer [3] .

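### The SAP's optional measure of the amount of IGF inhibition, mean percentage change in staining, is undefined at a zero baseline, is dominated by men with low baselines, and can understate or reverse a true fall

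*SAP*

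**What the plan says.** SAP 6 says that, depending on how the review of the HALO data turns out, "we may use mean percentage change in one or both markers to quantify the amount of IGF axis inhibition". It then commits to a use for that quantity: "This measure will be used in correlation analyses with research/tertiary endpoints in both the entire population and in pre-defined subgroups".

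The scale is set in SAP 4.1.1. H-Scores are built "to generate a score range of 0-300". If staining is too weak for that, "percentage of positively stained cells will be used as output instead".

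The formal primary analysis is separate. Under SAP 4.1.1, "the PRE/POST HALO scores will be analysed using a paired t-test", with the Wilcoxon matched-pairs test if the differences are not normal. The population-level summary in SAP Table 1 is "Statistical significance of the difference between IGF1 axis activity in PRE and POST treatment samples", which is a test result and not an amount.

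Tertiary objective 4 in the protocol synopsis is to "Correlate changes in IGF-1R expression, IGF axis activity with baseline and post-treatment cancer profile", so the change measure is meant to be set against baseline markers.

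SAP Table 1 excludes men whose samples cannot give a score. A score of 0 is still a score, and no rule covers it.

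**The concern.** Percentage change divides by the PRE score. It cannot go below -100%, has no upper limit, and does not exist at PRE = 0. A few men with weak baseline staining can therefore decide the average. Low baselines are most likely on the percent-positive scale, which the SAP keeps for weak staining.

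Two things are at stake. The first is the reported amount of inhibition, for which the SAP text names no other measure. The second is the biomarker work, because PRE enters the change measure and some candidate markers are read on the same diagnostic core. In addition, the choice of measure, and of one marker or both, is left until after the HALO data have been reviewed.

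**Working it through.** **1. The plan's own figure.** Inputs from SAP 3.2: effect size 0.68, Wilcoxon signed-rank, alpha 0.05, 80% power. Using noncentral-t paired power with asymptotic relative efficiency 3/pi, 20 pairs have an effective size of 20 x 0.955 = 19.1 and two-sided power 0.803. Sixteen pairs give one-sided power 0.812. The effect size of 0.6 with 24 pairs (paired t) gives 0.804. All reproduce, and none uses percentage change.

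**2. Leverage of one low baseline (arithmetic only).** One man goes from 5 to 25: (25 - 5)/5 = +400%. Four men go from 150 to 0: -100% each. The mean percentage change is (400 - 400)/5 = 0%. The group mean goes from (4 x 150 + 5)/5 = 121 to 25/5 = 5, a change of 5/121 - 1 = -96%.

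**3. Additive error (assumed values).** True baseline T is normal, PRE = T + error and POST = 0.7T + error. Scores are held to 0-300, men with PRE = 0 are dropped, and each trial has 20 men. The true fall is 30%.

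| Mean / between-man SD / error SD | At least one PRE = 0 | Average of mean % change | Median trial | Change in group mean | Geometric ratio, c = 1 to c = 10 |
|---|---|---|---|---|---|
| 150 / 40 / 20 | 0.8% | -28% | -28% | -30% | -31% to -29% |
| 100 / 40 / 30 | 35% | about +14% | -20% | -29% | -34% to -28% |
| 60 / 30 / 20 | 57-59% | about +29% | -18% | -29% | -32% to -25% |

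The +14% and +29% are not stable quantities. The density of PRE is positive next to 0, so the mean of 1/PRE does not exist, and repeated runs gave +7% to +34% and +21% to +36%. Rounding scores to whole points gave about -10% and -8%. The median trial is steadier. In rows two and three, about 19% and 25% of trials showed no fall at all.

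**4. Proportional error (assumed log-SD s in each sample).** Expected percentage change = 100 x (R x exp(s^2) - 1). For R = 0.7:
- s = 0.2: -27%
- s = 0.3: -23%
- s = 0.5: -10%
- s = 0.7: +14%

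**5. Correlations with no true association (assumed).** There are 24 men, between-man log-SD 0.5, error log-SD 0.35, and every man has a 30% fall. The table gives the share of trials significant at a nominal 5%.

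| Baseline marker | Percentage change | Log ratio | log POST on log PRE + marker |
|---|---|---|---|
| The marker's own (log) PRE score | about 48% | about 52% | not applicable |
| Shares PRE-core error, correlation 0.3 / 0.6 with observed PRE | 8-9% / 20% | 9% / 21% | 5% / 5% |
| Tied only to the true tissue level, correlation 0.3 / 0.6 / 0.8 | about 5% throughout | about 5% throughout | 8-9% / 20-21% / 45-47% |

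The false correlation is regression to the mean, and the log ratio shares it. Adjusting for PRE removes it where error is shared. Where the marker tracks the true level and PRE is noisy, the same adjustment creates a false association.

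**6. The constant c (assumed example).** Four of 20 men go from 150 to 0 and 16 are unchanged, so the group mean falls 20%. The geometric ratio is (c/(150 + c))^(4/20). Its change is -63% at c = 1, -50% at c = 5 and -43% at c = 10.

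**The case against.** The measure is optional, its stated use is exploratory correlation, and SAP 1 permits data transformation. Detail is deferred to the Data Definitions and Tables document, which was not available and may hold a formula and a zero rule. The phrase itself is ambiguous: it could mean the percentage change in means, which is nearly unbiased in the table above. With well-stained tissue and small error the distortion is about 2 points. All of this stands, and it limits how strongly the point can be put. It does not remove the gap in the SAP text. Correlation needs one value per man, so individual percentages are the natural reading, and the SAP itself gives no formula or low-baseline rule.

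A reader might infer four stronger things that the documents do not support:
- **The primary result is compromised.** It is not. The paired test and the sample size do not use percentage change.
- **Percentage change always understates a fall.** That depends on the form and size of the error, which are not given. If the spread is real variation in response, the arithmetic mean is a different summary and not a biased one.
- **All baseline correlations are spurious.** The problem needs error shared with the PRE core. Baseline serum IGF-1, measured in blood, is not affected in this way.
- **A log ratio or baseline adjustment is a complete cure.** Steps 5 and 6 show that neither is.

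**Conclusion.** The point holds as a weakness in an optional but only named measure of amount. That it is undefined at PRE = 0 and dominated by low baselines follows from the scale and needs no error model. Understatement or reversal is conditional. For a true 30% fall it ranges from about 2 points of understatement (mean 150, error SD 20) to a typical trial reading of -20% or -18%, with simulated averages above zero, at the lower assumed baselines. The error SDs and baseline means are assumptions throughout. The correlation concern is limited to markers sharing error with the PRE core. It is not specific to percentage change, and no single analysis is safe under every error structure.

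**What to change.** Amend SAP 6 before the PRE/POST results are reviewed.

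- **Magnitude.** Replace mean percentage change with one fixed measure and its 95% CI, and state whether it applies to one marker or both. Use either the percentage change in the group mean (mean POST / mean PRE - 1, bootstrap CI), or the geometric mean POST/PRE ratio with c fixed in advance and a sensitivity analysis over c. The first needs no constant.
- **Per-man value in correlations.** Use the paired difference or the log ratio.
- **Markers read on the same PRE core.** Report both the association with the change score and the baseline-adjusted one (log POST on log PRE plus the marker). Treat an association as supported only if the two agree, since each is biased under a different error structure. Markers with independent error, such as serum IGF-1, do not need this double check.

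The data are unchanged. The cost is SAP wording, some extra analysis and, if the geometric ratio is chosen, committing to c in advance.

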## 6.1 Outcome Definitions

*Provide a simple list of all primary and secondary outcomes, together with time-points at which they are collected, with full details of definitions, and how these outcome variables will be generated and reported as provided in SAP - Data Definitions and Tables which should be cross-referenced.*

	Objectives	Endpoints
Primary endpoint	Assess the amount of IGF pathway inhibition induced by xentuzumab	Phospho-IGF-1R and phospho-S6 immunohistochemistry on tissue from biopsy and prostatectomy
Secondary endpoints	1. Feasibility of treatment in pre-operative setting 2. Assess safety and tolerability of xentuzumab administered in the pre-prostatectomy setting	1. Number of patients whose radical prostatectomy is performed within 7 days of the 4 th dose of xentuzumab (patients can receive up to 10 doses of xentuzumab if surgery is delayed) 2. Treatment-related adverse events scored using NCI-CTCAE v5.0
Tertiary/exploratory endpoints	1. Assess change in PSA following administration of xentuzumab in the pre-prostatectomy setting 2. Assess changes in tissue markers following administration of xentuzumab in the pre-prostatectomy setting 3. Assess changes in circulating markers following administration of xentuzumab in the pre-prostatectomy setting 4. Correlate changes in IGF-1R expression, IGF axis activity with cancer profile which may include mutation analysis, gene expression and phosphoproteomic profile	1. Change in serum PSA 2. Changes by IHC on FFPE tissues in tissue markers (e.g. Ki67 index, IGF-1R, RRM2, CD31, immune markers: PD-L1, CD4, CD8, FoxP3) 3. Changes in circulating markers of endocrine response to IGF blockade (e.g. IGF-1, insulin, IGFBPs, circulating IGF bioactivity, plasma metabolomic profile) 4. Tumour profiling (e.g. gene mutation panel, IHC for PTEN, FISH for TMPRSS2-ERG, transcriptional and phospho-proteomic profile of index tumour)

Table 3. Definition of WINGMEN outcomes.

